9.3	RISK BENEFIT ASSESSMENT	16
9.4	INFORMED CONSENT PROCESS / HIPAA AUTHORIZATION.....	16
10	STUDY FINANCES.....	16
10.1	FUNDING SOURCE	16
10.2	CONFLICT OF INTEREST	16
10.3	SUBJECT STIPENDS OR PAYMENTS	16
11	PUBLICATION PLAN.....	16
12	REFERENCES.....	16
13	ATTACHMENTS	17

CONFIDENTIAL

Study Summary

Title	Prospective Evaluation of Infraorbital Filler
Short Title	Infraorbital Filler Study
IRB Number	TBD
Protocol Number	TBD
Methodology	Prospective Case Series / Descriptive Study
Study Duration	3 months
Study Center(s)	Single-center
Objectives	To quantify under eye volume changes over time and patient satisfaction with infraorbital dermal filler injections
Number of Subjects	Approximately 10
Main Inclusion and Exclusion Criteria	
Inclusion criteria:
 
1) Female2) Age 22-653) Interested in filler injections to reduce undereye volume loss4) Participants must sign the informed consent form 
Exclusion:
 
1) Prior filler in tear trough/midface2) Filler/neurotoxin injection within the past 12 months or during duration of study3) Prior facial cosmetic surgery (ie. facelift)4) Prior facial trauma (ie. orbital fracture)5) Pregnant or breastfeeding

CONFIDENTIAL

This material is the property of the University of Pennsylvania.

Intervention	Injection of Juvéderm Volbella XC into undereye/infraorbital region
Statistical Methodology	Descriptive statistics will be used to describe changes in volume over time and PRO's
Data and Safety Monitoring Plan	PI: [name] will oversee the study, protocol, and data monitoring and storage.

Background and Study Rationale

1 Introduction

This study will be conducted in full accordance with all applicable University of Pennsylvania Research Policies and Procedures and all applicable Federal and state laws and regulations.

The purpose of the study is to use 3D imaging to evaluate the effects of Juvéderm Volbella XC filler that is FDA approved for injection in infraorbital region. Participation is available to women ages 22 to 65 who have never received filler injections. All subjects will undergo 3D imaging using the VECTRA M3 (Canfield Scientific, Inc, Fairfield, NJ) prior to treatment with a Juvéderm filler in order to determine their baseline volumetric measurements and dimensions. Imaging will be repeated post injection to determine change over time (over a 3-month time period).

1.1 Background and Relevant Literature

Juvéderm Volbella XC is a gel implant or dermal filler that consists of crosslinked hyaluronic acid made by a Streptococcal bacteria species intended to temporarily add fullness to the facial soft tissues. It was originally approved for injection into the lips for lip augmentation and correction of perioral rhytids. It has since been FDA-approved for injection into the undereye hollows to improve the appearance of undereye hollows in adults over the age of 21 [1].

The “Zoom Effect” describes the recent upsurge in demand for cosmetic procedures during the COVID-19 pandemic. The reason for this appears to be that people are now constantly seeing their own and other faces on the screen, making them particularly conscious of potential facial irregularities, aging changes, and asymmetries. According to statistics from the Aesthetic Society, facial procedures have increased 55% in 2021 [2]. Soft tissue filler injections are the 2nd most common non-surgical cosmetic procedure performed in the US and have increased 42% in 2021 [2,3].

Undereye or infraorbital hollowing is a result of a loss of volume causing shadowing and darkness of the infraorbital region often interpreted as a tired, stressed, and aged appearance. The Allergan Infraorbital Hollows Scale is a validated scale for objective and reproducible comparisons of infraorbital hollows

CONFIDENTIAL

before and after dermal filler injection [4]. The Tear Trough Rating Scale (TTRS) is another validated method of evaluating tear trough deformities that measures depth of trough, degree of hyperpigmentation, prolapse of nasal fat pads/pockets, and lower eyelid skin rhytidosis [6]. 3D photogrammetry technology allows for high level feature enhancement and microscopic anatomical evaluation that was not previously possible and can be used to make volumetric measurements at injection sites to evaluating minimally invasive injection efficacy. [7-9]. In this study, we aim to use these volumetric measurements to describe undereye volume after infraorbital dermal filler injection and further understand the behavior of the product in soft tissues over time.

2 Study Objectives

2.1 Primary Objective

The primary objective of the study is to quantify and describe under eye volume changes over time after infraorbital hyaluronic acid filler injections.

3 Investigational Plan

3.1 General Design

This study is a prospective case series/descriptive study – 10 patients will be enrolled to receive hyaluronic acid filler injections (Juvéderm Volbella XC). Each patient will receive FDA approved dosages of filler to the infraorbital region to treat undereye, as per FDA approved indications. All injections will be performed by an Allergan-trained physician ([name], PhD) according to a preset injection plan per FDA approved administration guidelines. Prior to injection patients will be imaged with 3-dimensional photogrammetry. Subjects will return post-injection in 2 weeks, 1 month, and 3 months for re-imaging. The study drug will be stored in a locked room that is only accessible to the research team.

3.2 Allocation to Interventional Group

All subjects will receive filler injections to the infraorbital region at standardized injection sites

3.3 Study Measures

3D photogrammetry imaging of each subject at the pre-determined time points will be obtained using the VECTRA M3 (Canfield Scientific, Inc., Fairfield, NJ) which allows for volumetric measurements. Three-dimensional coordinates will be calculated to generate each subject's topographic configuration, displacement, and volume of each detected point on the surface of the face relative to its original reference image.

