3.4 Study Endpoints

3.4.1 Primary Study Endpoint

The primary endpoint is volume changes of the infraorbital area over time after injection of filler quantified using 3D facial imaging measurements.

CONFIDENTIAL

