4.1 Duration of Study Participation

The duration of study participation is 90 days. Subjects will receive injections on day 1, and follow up imaging will occur on day 14, 30, and 90 post intervention. Each individual subject's participation time in the study will consist of the duration of the initial imaging session (approximately 20 minutes), procedure (15 minutes), follow up imaging (20 min).

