5.1 Screening

The screening visit involves patient evaluation of inclusion and exclusion criteria. This information is readily available on the intake visit and does not deviate from standard of care for a clinic visit, including

CONFIDENTIAL

age and past medical history. Once patients are deemed eligible, the process of informed consent will begin. Informed consent will take place.

5.2 *Study Intervention or Observational Phase*

5.2.1 **Visit 1 (sometimes referred to as the baseline visit)**

Visit 1 involves screening, consent, baseline imaging, randomization, intervention. The subject will be photographed using 3D imaging to measure baseline undereye volume. After these images, subjects will complete a FACE-Q questionnaire and then be injected with Juvéderm Volbella XC filler in the infraorbital region according to a preset injection plan per FDA approved administration guidelines. Medication will be prepared as described on the FDA approved medication guide. A second set of 3D images will be taken after filler injection to measure starting infraorbital volume.

5.2.2 **Visit 2**

Visit 2 which will occur 14-days post-injection, will consist of a repeat of the above measurements using 3D imaging. Subjects will also complete the FACE-Q via electronic REDCap survey and communicate any questions or concerns.

5.2.3 **Visit 3**

Visit 3 which will occur 30-days post-injection, will consist of a repeat of the above measurements using 3D imaging. Subjects will also complete the FACE-Q via electronic REDCap survey and communicate any questions or concerns.

5.2.4 **Visit 4**

Visit 4 which will occur 90-days post-injection, will consist of a repeat of the above measurements using 3D imaging. Subjects will also complete the FACE-Q via electronic REDCap survey and communicate any questions or concerns.

TABLE 1 SCHEDULE OF STUDY PROCEDURES

	Baseline Visit 1	Intervention	Follow-up Visit 2 Day 14	Follow-up Visit 3 Day 30	Follow-up Visit 4 Day 90
Visit Window	Day 1	Day 1	Day 14 ± 5	Day 30 ± 5	Day 90 ± 7
Eligibility	X				
Informed Consent	X				
Demographic	X				
Medical History	X				
Consultation	X				
Vectra Photography		X (pre and post injection)	X	X	X

CONFIDENTIAL

FACE-Q		X	X	X	X
Adverse Events		X	X	X	X

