6.1 Sample Size and Power Determination

The sample size of this case series will be 10 female patients between the ages 22 and 65.

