6.3.2 Analysis of Primary Outcome of Interest

The primary analysis of volumetric measurements will be done using the Allergan Infraorbital Hollow Scale and the Tear Trough Rating Scale.

7 Safety and Adverse Events

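### No repeat 3D captures are required; if one pre-injection capture is the reference, its error is shared by all four gains, and averaging three captures per session would cheaply reduce it

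*Combined protocol and SAP*

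**What the plan says.** Section 3.3 (Study Measures) obtains the "volume of each detected point on the surface of the face relative to its original reference image". The reference is in the singular. The section does not say when it is taken or how many captures lie behind it.

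Section 3.1 places imaging before injection, and section 5.2.1 (Visit 1) gives the order: "The subject will be photographed using 3D imaging to measure baseline undereye volume", then "After these images, subjects will complete a FACE-Q questionnaire", then the injection, and then "A second set of 3D images will be taken after filler injection to measure starting infraorbital volume". Section 4.1 adds that "follow up imaging will occur on day 14, 30, and 90 post intervention". Each woman therefore has one pre-injection and four post-injection imaging time points.

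The primary endpoint in section 3.4.1 is an imaging measure: "The primary endpoint is volume changes of the infraorbital area over time after injection of filler quantified using 3D facial imaging measurements". Section 6.3.2 assigns the analysis elsewhere: "The primary analysis of volumetric measurements will be done using the Allergan Infraorbital Hollow Scale and the Tear Trough Rating Scale". Section 6.1 sets the size: "The sample size of this case series will be 10 female patients between the ages 22 and 65". Section 6.2 limits the analysis to description.

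No section gives a number of captures per session, a rule for averaging them, or a figure for imaging repeatability. Section 6.3, on control of bias, deals only with product and injection location.

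**The concern.** A surface capture carries random error, for instance from small movements of the lid or cheek. If one pre-injection capture is the reference for gain, its error is subtracted from every later measurement of that woman. All four gains then move together, and the result looks like a sustained effect rather than noise. The later visits cannot expose this, because they share the reference.

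Three results would be affected: the level of gain over baseline in each woman, any percentage of the immediate gain still present at a later visit, and each woman's value in the first secondary endpoint (section 3.4.2), which correlates satisfaction with volume change. Without a repeatability figure, a reader of a 10-woman case series cannot judge how much of one woman's curve is measurement error.

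**Working it through.** The plan has no figure to reproduce: N = 10 is stated without a calculation, and no imaging error is given. The check therefore works in units of e, the error SD of one capture.

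**Inputs from the documents.** 10 women (6.1); five imaging time points per woman, one before and four after injection (4.1, 5.2.1).

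**Assumptions.** Capture errors have mean zero and the same SD e. They are independent at first; this is relaxed in step 4.

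**1. One capture per session.** The error of the gain at time t is e_t − e_0.
- Variance: e² + e² = 2e², so the SD is 1.41e.
- Covariance between two gains: e², from the shared reference, so the error correlation is e²/(2e²) = 0.5.

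**2. Where the reference error goes.**
- Difference between two post-injection visits: (e_t − e_0) − (e_s − e_0) = e_t − e_s. The reference error cancels.
- Retention ratio: take a true retention of 0.80 and an immediate gain of 1 (both assumed). A reference error of size d gives (0.80 − d)/(1 − d) or (0.80 + d)/(1 + d). For d = 0.10 these are 0.78 and 0.82; for d = 0.30 they are 0.71 and 0.85. It does not cancel.
- Mean of 10 women: the errors are independent between women, so the mean is not biased. Its error SD is 1.41e/√10 = 0.45e, of which the reference contributes e/√10 = 0.32e.

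**3. Averaging m captures, independent errors.** At every session the SD of a gain is √(2/m)·e.

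| Captures | SD of a gain | Reduction |
|---|---|---|
| 1 at every session | 1.41e | – |
| 2 at every session | 1.00e | 29% |
| 3 at every session | 0.82e | 42% |
| 3 of the reference only: √(1 + 1/3)·e | 1.15e | 18% |

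Three at every session also lowers the SD of a visit-to-visit difference from 1.41e to 0.82e. Three of the reference alone leaves it at 1.41e.

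**4. Part of the error belongs to the session.** Pose, expression or swelling on the day may be common to all captures of a session. If a share r of the error variance is of this kind, three captures at every session give an SD of √(2[r + (1 − r)/3])·e.
- r = 0.25: 1.00e, 29% less.
- r = 0.50: 1.15e, 18% less.
- r = 0.75: 1.29e, 9% less.

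**5. Size relative to the effect.** If e is 10% to 30% of the immediate gain (assumed), the error SD of one woman's gain is 14% to 42% of that gain with single captures (1.41 × 10% and 1.41 × 30%). With three independent captures it is 8% to 24% (0.816 × 10% and 0.816 × 30%).

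**6. Workload.** Captures: 10 × 5 = 50 now, 10 × 5 × 3 = 150 with three. Comparisons with the reference: 10 × 4 = 40 now. Pairing each follow-up capture with a different reference capture gives 40 × 3 = 120, and the mean of the three pairs has the same SD of 0.82e under independence.

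**The case against.** The strongest reply is that a single-capture design is not in the documents. Section 3.3 does not state a number, and section 5.2.1 uses plurals for the Day 1 images. A reader might infer from the singular in section 3.3 that one capture is certain. The text does not go that far; the plurals could mean several captures or several views of one. This stands, and it makes the point conditional. It does not remove it, because under neither reading does the plan require that several captures be measured and averaged.

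A reader might also infer that every reported change is distorted. That is not supported. Section 5.2.1 treats the immediate post-injection set as the starting volume, so later loss may be taken from there, and the reference error cancels in any such difference. The absolute course of loss after injection is untouched.

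Third, the errors are noise in the 10-woman mean, and the benefit depends on how much error is common to a session. Both stand. Repositioning between captures deals with only part of the session component.

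Fourth, averaging might seem costly, since comparing all three follow-up captures with all three reference captures needs nine comparisons per time point, or 360 in total. Pairing avoids this. It remains true that no capture or measuring time is documented, so low cost is plausible rather than shown. The one relevant figure is an initial imaging session, and follow-up imaging, of about 20 minutes each (section 4.1).

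Finally, section 6.3.2 rests the primary analysis on two rating scales that do not use the reference image. That conflict matters more than imaging precision and needs resolving, but imaging volume remains the stated primary endpoint.

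**Conclusion.** The point holds as a cheap improvement, not as an error in the plan. If one pre-injection capture is the reference, its error is shared by all four gains over baseline (correlation 0.5) and makes up half of the capture-error variance of each. It affects the level of gain, retention percentages and the satisfaction correlation.

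Three captures at every session would reduce the error SD of a gain by 42% at best, and by 9% to 29% if a quarter to three quarters of the error variance is session-level. The absolute size cannot be stated, because the documents give neither e nor an expected gain. The conclusion rests on the pre-injection image being the reference, which is the natural reading of sections 3.1, 3.3 and 5.2.1 but is not written out.

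**What to change.** In sections 3.3 and 5.2:

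1. Name the pre-injection set as the reference for gain. State separately whether later loss is also measured from the immediate post-injection set.
2. Take three captures at each session, with repositioning between them.
3. Compare each follow-up capture with a different reference capture, and average the three results.
4. Report the within-session SD beside the volume changes, labelled as within-session repeatability only. It leaves out pose, expression and other effects of the day, so it understates the error between visits.

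Separately, reconcile sections 3.4.1 and 6.3.2 so that the primary analysis uses the imaging volumes, with the two scales as the secondary endpoints that section 3.4.2 makes them.

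The cost is about 150 captures against 50 and 120 comparisons against 40, with no extra visit. If the sets already hold several captures, the added work is mainly measuring. The change should be made before enrolment, because a missing pre-injection repeat cannot be obtained once filler has been injected.

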3.4 Study Endpoints

3.4.1 Primary Study Endpoint

The primary endpoint is volume changes of the infraorbital area over time after injection of filler quantified using 3D facial imaging measurements.

CONFIDENTIAL

3.4.2 Secondary Study Endpoints

- 1) Correlation of patient satisfaction with undereye volume changes as determined by PRO's (via FACE-Q)
- 2) Allergan Infraorbital Hollow Scale

TABLE 1. Allergan Infraorbital Hollows Scale Descriptors		
Grade	Term	Descriptor
0	None	No visible hollowing or volume loss medially or laterally
1	Minimal	Presence of hollowing with some volume loss medial to the mid-pupillary line; smooth lateral lid-cheek transition
2	Moderate	Defined hollowing extending laterally beyond the mid-pupillary line with moderate volume loss; smooth lateral lid-cheek transition with mild volume loss
3	Severe	Defined hollowing extending laterally beyond the mid-pupillary line with moderate volume loss creating a defined groove along the lid-cheek junction
4	Extreme	Defined hollowing extends from medial to lateral canthus; severe volume loss creates a marked step along the lid-cheek junction

[figure not shown]
[figure not shown]

Figure 2. Assessment guide for the Allergan Infraorbital Hollows Scale.

- 3) Tear Trough Rating Scale

TTRS

The tear trough was assessed based on multiple characteristics defined by a novel TTRS. The multicontoured area of the tear trough is the additive product of multiple factors. Each separate component was evaluated individually, and the score was totalled. The factors accounted for the evaluation scale are described below:

- Depth of the trough – distance from the anterior lacrimal crest to the depth of the trough; each millimeter of depth is given 1 point (i.e., a prominent trough with a 3-mm depth is given 3 points)
- Hyperpigmentation – dyspigmentation, while not directly contributing to the depth of the trough, creates an illusion of depth; no hyperpigmentation is given 1 point; mild is given +2 points; moderate pigmentation is given +3 points; and intense or deep hyperpigmentation is given 4 points; subdermal dark casting caused by venous pooling can be graded as hyperpigmentation.
- Prolapse of nasal fat pads/pockets – prominent prolapse of the nasal fat pad accentuates the depth of the trough and was rated as mild (1 point), moderate (2 points), or severe (3 points).
- Lower eyelid skin rhytidosis accentuates the fatty prolapse and the depth of the trough – skin rhytidosis is rated 1+ to 4+ (mild, moderate, advanced, severe – according to Glogau's scale); 1+ is given 1 point, and 4+ is given 4 points

Because tear troughs are often asymmetric, both sides should be evaluated individually.

4 Study Population and Duration of Participation

4.1 Duration of Study Participation

The duration of study participation is 90 days. Subjects will receive injections on day 1, and follow up imaging will occur on day 14, 30, and 90 post intervention. Each individual subject's participation time in the study will consist of the duration of the initial imaging session (approximately 20 minutes), procedure (15 minutes), follow up imaging (20 min).

4.2 Total Number of Subjects and Sites

We anticipate about 10 patients from at a single location, the Hospital of the University of Pennsylvania. Subjects will include females, ages 22-65, who are interested in infraorbital filler injection (FDA approved use).

4.3 Inclusion Criteria

Adult female subjects, ages 22-65, who are interested in infraorbital filler injection FDA approved use. Each participant will participate for 90 days.

- Female
- 22-65 years of age
- Interested in filler injections to reduce undereye volume loss
- Participants must sign the informed consent form

4.4 Exclusion Criteria

- Female under 22 or above 65 years of age
- Male
- Prior filler in tear trough/midface
- Filler/neurotoxin injections within 12 months or during duration of study
- Prior facial cosmetic surgery
- Prior facial trauma (ie. orbital fracture)
- Pregnant or breastfeeding

4.5 Subject Recruitment

Patients will be recruited through the plastic surgery clinic, which is a high-volume practice for those who may be interested in cosmetic injections. Additionally, we plan to use of a flyer posted throughout the health system and campus. Filler injections to the infraorbital region to reduce undereye volume loss are a popular procedure and we do not anticipate significant difficulty in recruiting about 10 willing participants.

4.6 Vulnerable Populations:

Children, pregnant women, fetuses, neonates, or prisoners are not included in this research study.

5 Study Procedures

5.1 Screening

The screening visit involves patient evaluation of inclusion and exclusion criteria. This information is readily available on the intake visit and does not deviate from standard of care for a clinic visit, including

CONFIDENTIAL

age and past medical history. Once patients are deemed eligible, the process of informed consent will begin. Informed consent will take place.

5.2 *Study Intervention or Observational Phase*

5.2.1 **Visit 1 (sometimes referred to as the baseline visit)**

Visit 1 involves screening, consent, baseline imaging, randomization, intervention. The subject will be photographed using 3D imaging to measure baseline undereye volume. After these images, subjects will complete a FACE-Q questionnaire and then be injected with Juvéderm Volbella XC filler in the infraorbital region according to a preset injection plan per FDA approved administration guidelines. Medication will be prepared as described on the FDA approved medication guide. A second set of 3D images will be taken after filler injection to measure starting infraorbital volume.

5.2.2 **Visit 2**

Visit 2 which will occur 14-days post-injection, will consist of a repeat of the above measurements using 3D imaging. Subjects will also complete the FACE-Q via electronic REDCap survey and communicate any questions or concerns.

5.2.3 **Visit 3**

Visit 3 which will occur 30-days post-injection, will consist of a repeat of the above measurements using 3D imaging. Subjects will also complete the FACE-Q via electronic REDCap survey and communicate any questions or concerns.

5.2.4 **Visit 4**

Visit 4 which will occur 90-days post-injection, will consist of a repeat of the above measurements using 3D imaging. Subjects will also complete the FACE-Q via electronic REDCap survey and communicate any questions or concerns.

TABLE 1 SCHEDULE OF STUDY PROCEDURES

	Baseline Visit 1	Intervention	Follow-up Visit 2 Day 14	Follow-up Visit 3 Day 30	Follow-up Visit 4 Day 90
Visit Window	Day 1	Day 1	Day 14 ± 5	Day 30 ± 5	Day 90 ± 7
Eligibility	X				
Informed Consent	X				
Demographic	X				
Medical History	X				
Consultation	X				
Vectra Photography		X (pre and post injection)	X	X	X

CONFIDENTIAL

FACE-Q		X	X	X	X
Adverse Events		X	X	X	X

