6.2 Statistical Methods

Descriptive statistics will be used to describe volume changes of undereye hollows over time. The results of this study will not have true statistical significance.

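### Does the primary volume endpoint leave open which Day 1 image the change is measured from?

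*Combined protocol and SAP*

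**What the plan says.** Visit 1 (5.2.1) has two image sets with different labels. For the first, "The subject will be photographed using 3D imaging to measure baseline undereye volume". The FACE-Q follows, then the injection, then the second set: "A second set of 3D images will be taken after filler injection to measure starting infraorbital volume". The schedule table lists Day 1 photography both before and after injection, then at Days 14, 30 and 90.

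The primary endpoint (3.4.1) is "volume changes of the infraorbital area over time after injection of filler", with no reference image named. Section 3.3 says the system yields "displacement, and volume of each detected point on the surface of the face relative to its original reference image". Section 1 states that imaging before treatment determines the baseline volumetric measurements, and continues: "Imaging will be repeated post injection to determine change over time (over a 3-month time period".

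The statistical sections add nothing on the reference. Section 6.2 reads "Descriptive statistics will be used to describe volume changes of undereye hollows over time", and 6.3.2 names two rating scales and no volume contrast. Secondary endpoint 1 (3.4.2) correlates FACE-Q satisfaction with the same volume changes.

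**The concern.** Baseline and starting are near-synonyms, and here they label two different volumes taken on the same day. Measured from the pre-injection image, change is the gain over the untreated face. Measured from the post-injection image, it is the departure from the freshly treated face. These are different quantities and can have opposite signs. The second also carries any same-day swelling in its starting value. Section 9.1 lists swelling as a side effect without giving its size or duration, and as it resolved it would be counted as lost product.

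In a descriptive series of about 10 patients the summary figures are the whole result. If the reference were truly open, the main figure could be chosen after the data were seen, and the FACE-Q correlation would follow that choice.

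**Working it through.** **1. What the text supports.** Three places favour the pre-injection image:

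- Section 1 ties the word baseline to imaging before treatment, and then describes repeat imaging as the way to determine change.
- Section 3.3 refers each surface point to the original image. The original is most naturally the first one taken.
- Section 5.2.1 puts the only Day 1 FACE-Q before the injection. A FACE-Q change score therefore has a matching volume only in the pre-injection image.

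No passage subtracts the starting volume from anything.

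**2. How the two versions relate.** Let V_pre and V_post be the Day 1 volumes and V_t the volume at a later visit. Then

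V_t − V_post = (V_t − V_pre) − (V_post − V_pre).

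Within a patient the versions differ by one constant, the Day 1 step. Differences between follow-up visits, such as Day 90 minus Day 14, are identical under both. Every term is scheduled to be imaged.

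**3. When the sign reverses.** Every input from here on is assumed, because the documents give none. Take the filler gain as 1 unit (volume changes scale with it; retention does not). Let r be the gain remaining at follow-up, with swelling resolved, and s the same-day swelling as a share of the filler gain. Change from pre-injection is r; change from post-injection is r − (1 + s). The signs are opposite only if 0 < r < 1 + s. With s = 0 and r = 1.1 the two are +1.10 and +0.10; with s = 0.3 and r = 1.4 they are +1.40 and +0.10. Both are gains in each case. Reversal is plausible but not certain.

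**4. Size when r = 0.75.** Apparent retention from the post-injection image is r/(1 + s).

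| s | Change from pre | Change from post | Apparent retention |
|---|---|---|---|
| 0 | +0.75 | −0.25 | 75.0% |
| 0.05 | +0.75 | −0.30 | 71.4% |
| 0.10 | +0.75 | −0.35 | 68.2% |
| 0.25 | +0.75 | −0.50 | 60.0% |
| 0.50 | +0.75 | −0.75 | 50.0% |

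Swelling adds one-for-one to the apparent loss. The shortfall in retention is r·s/(1 + s): at s = 0.10 it is 4.5, 6.8 or 8.2 percentage points for r = 0.50, 0.75 or 0.90.

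**5. The FACE-Q correlation.** Suppose every patient has the same filler gain, r and s are independent, and satisfaction follows visible gain with a correlation of 0.60. Using the post-injection reference would then give 0.60 × SD(r)/√(SD(r)² + SD(s)²):

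| SD(r) | SD(s) = 0.05 | SD(s) = 0.10 | SD(s) = 0.20 |
|---|---|---|---|
| 0.05 | 0.42 | 0.27 | 0.15 |
| 0.10 | 0.54 | 0.42 | 0.27 |
| 0.20 | 0.58 | 0.54 | 0.42 |

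The answer depends heavily on SD(r), which is unknown, and the formula fails if gains differ between patients. For scale, an observed correlation of 0.60 with n = 10 has an approximate 95% Fisher interval of tanh(0.693 ± 1.96/√7), or −0.05 to 0.89. Every entry in the table lies inside it.

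**The case for a change.** The case for a change is that no passage states the reference outright, and some wording leans the other way. The endpoint speaks of change after injection. Section 1.1 aims to understand how the product behaves in tissue over time, which suits a post-injection origin. Starting ordinarily means the origin of a time course, and the protocol never says what that volume is for. Visit 1 as a whole is also called the baseline visit, so even change from the baseline visit would not separate the two image sets. Naming the reference would cost one sentence.

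Much of this stands. The definition is unwritten, the label is unfortunate, and swelling would distort a loss figure taken from the post-injection image. But these are hints from word choice, set against passages that describe how baseline and reference are obtained. The post-injection image also has a legitimate descriptive use for the aim in 1.1, provided possible swelling is mentioned, so its presence in the schedule does not show that it was meant as the primary reference. Writing the reference down would record the likely reading and would not alter the analysis under it.

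The use of rating scales in 6.3.2 to analyse volumes ("The primary analysis of volumetric measurements will be done using the Allergan Infraorbital Hollow Scale and the Tear Trough Rating Scale") is a separate matter that naming a reference image would not settle.

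**Conclusion.** No change follows. The gap is real but small, and an analyst reading Sections 1, 3.3 and 5.2.1 together would measure change from the pre-injection image. On that reading the reference value precedes the injection and so carries none of its swelling, and the volume change lines up with the pre-injection FACE-Q. If a reader wants the other contrast, the scheduled images supply it.

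The possible harm is conditional. A gain turns into a decline only if the post-injection image is chosen and follow-up volume lies between the two Day 1 volumes. The loss of 4 to 25 percentage points of apparent retention (75% falling to between 71% and 50%) rests on assumed r = 0.75 and swelling of 5% to 50% of the filler gain. The FACE-Q attenuation rests on further assumed spreads and is small beside the sampling error of a correlation in 10 patients. The study is descriptive and 6.2 disclaims statistical significance, so no error rate or sample-size figure is affected. The conclusion would differ if any passage defined change from the starting volume; none does.
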